1.0 Objectives

1.1 Describe the purpose, specific aims, or objectives of this research.

Response: To study the effects of liraglutide (a drug used to treat type 2 diabetes) on glucose (sugar) control over the 26 week study period when used in addition to insulin. The use of Liraglutide in Type 1 Diabetes is investigational

1.2 Describe the purpose, specific aims, or objectives.

Response:

Aim 1.1: To compare the mean HbA1c, fasting glucose, weekly glucose, the standard deviation of weekly blood glucose concentrations as recorded by continuous glucose monitoring, fructosamine and the dose of insulin required prior to and following 26 weeks of treatment with liraglutide.

Aim 1.2: To compare the postprandial glucose concentrations following a test meal before and after 26 weeks of treatment with liraglutide.

Aim 2.1: To compare the basal and postprandial glucagon and C-peptide concentrations following a test meal before and after 26 weeks of treatment with liraglutide.

Aim 3.1: To compare ROS generation, TBARS, intranuclear NF κ B binding in MNC, the expression of TLR-4, TNF α , I κ B α , MMP-9, SOCS-3, PKC β II, PTP-1B, GSK-3 β , IKK β , JNK-1, I κ B and pI κ B in MNC and adipose tissue and plasma concentrations of CRP, MCP-1, PAI-1, TNF α , RANTES, free fatty acids (FFA) prior to and following: a) a single injection of liraglutide 1.2mg at first study visit; b) treatment with liraglutide for 26 weeks.

Aim 3.2: To compare the changes in NF κ B binding and the expression of TLR-4, TNF α , I κ B α , SOCS-3, PTP-1B, PKC β II, IKK β and JNK-1 in MNC following a standard meal challenge prior to and after 26 weeks of treatment with liraglutide..

Aim 4.1: To assess subcutaneous fat mass, hepatic fat content and visceral fat mass by MRI of abdomen and DEXA before and 26 weeks after treatment with liraglutide.

Aim 4.2: To assess change in waist circumference, blood pressure, triglycerides, HDL cholesterol and incidence of metabolic syndrome after treatment with liraglutide

Aim 5.1: To compare the gastric emptying as measured by acetaminophen absorption before and 26 weeks after treatment with daily subcutaneous liraglutide injection.

Aim 6.1: To compare the blood pressure using a 24 hour blood pressure monitor before and 26 weeks after treatment with liraglutide.

Aim 6.2: To compare endothelial function by measuring flow mediated dilatation (FMD) in brachial artery before and 26 weeks after treatment with liraglutide.

Aim 7.1: To compare the quality of life questionnaire scores and depression questionnaire scores before and 26 weeks after treatment with liraglutide

1.3 State the hypotheses to be tested, if applicable.

NOTE: A hypothesis is a specific, testable prediction about what you expect to happen in your study that corresponds with your above listed objectives.

Response:

Hypothesis 1: Treatment with Liraglutide in overweight or obese patients with type 1 diabetes decreases fasting, postprandial and the overall mean glucose concentrations while decreasing the dose of insulin required.

Hypothesis 2: Treatment with Liraglutide decreases basal and postprandial glucagon concentrations and increases basal and postprandial C-peptide concentrations.

Hypothesis 3. Treatment with liraglutide suppresses indices of oxidative and inflammatory stress including the mediators of insulin resistance, in peripheral blood mononuclear cells (MNC), plasma and adipose tissue.

Hypothesis 4: Treatment with liraglutide reduces abdominal adiposity, hepatic and visceral fat mass and improves features of metabolic syndrome.

Hypothesis 5: Treatment with Liraglutide in obese patients with type 1 diabetes delays gastric emptying.

Hypothesis 6: Treatment with Liraglutide in obese patients with type 1 diabetes improves blood pressure and endothelial function.

Hypothesis 7: Treatment with Liraglutide in obese patients with type 1 diabetes improves quality of life and depression as measured by questionnaires.

2.0 Scientific Endpoints

2.1 Describe the scientific endpoint(s), the main result or occurrence under study.

NOTE: Scientific endpoints are outcomes defined before the study begins to determine whether the objectives of the study have been met and to draw conclusions from the data. Include primary and secondary endpoints. Some example endpoints are: reduction of symptoms, improvement in quality of life, or survival. Your response should **not** be a date.

Response: **Primary endpoint:** Change from baseline in HbA1c at 26 weeks as compared to placebo. **Secondary endpoints:** Change from baseline as compared to placebo in a)fasting and postprandial blood sugars, mean weekly glucose concentrations, standard deviation of weekly blood sugars and fructosamine; b)fasting and postprandial glucagon and C-peptide concentrations; c)insulin doses; d)indices of oxidative and inflammatory stress in MNC, plasma and adipose tissue; e)oxidative and inflammatory stress in plasma

and MNC following meal challenge; f)subcutaneous fat mass, hepatic fat content and visceral fat mass; g)waist circumference, blood pressure, triglycerides, HDL cholesterol and incidence of metabolic syndrome; h)gastric emptying; i) 24 hour blood pressure; j) flow mediated dilatation in brachial artery, k) SF-36 score; l) depression (PHQ) score.

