17.0 Data Management and Analysis

17.1 Describe the data analysis plan, including any statistical procedures. This section applies to both quantitative and qualitative analysis.

Response: The focus of the proposed research is to evaluate the effect of liraglutide on mean HbA1c% over the period of 26 weeks of treatment. The similarities between the study groups, baseline values for subject's demographics and study endpoints will be compared using appropriate parametric tests. Transformations of the data in order to meet statistical assumptions may be considered. The **primary endpoint** of the study is to detect

a difference in HbA1c after 26 weeks of treatment with Liraglutide or placebo. The statistical analysis will be carried out using analysis of covariance (ANCOVA) and tested at the 0.05 level. Change in weight will be a covariate. The results will be computed as mean \pm SD. Analysis will be carried out on the basis of intention to treat (with last observation carried forward).

The secondary end points based on glycemic changes will include the difference from baseline in mean weekly glucose concentrations, standard deviations of the mean weekly glucose concentrations, HbA1c, fructosamine, the duration of time spent in hyperglycemia ($>150\text{mg/dl}$, $>200\text{mg/dl}$, $>250\text{mg/dl}$) and hypoglycemia ($<70\text{mg/dl}$, $<40\text{mg/dl}$), insulin dosage. A reduction in the AUC following the meal will constitute another secondary end point. Between groups comparisons of the magnitude of change from baseline will also be made for these glycemia related secondary endpoints using student's t-test. Comparisons for these and the primary endpoints will also be made using the paired t-test or Wilcoxon's test for paired data within each group.

The other secondary end-points of the study will be change from baseline after 26 weeks of treatment in the fasting and postprandial blood sugars, glucagon and C-peptide concentrations, indices of oxidative and inflammatory stress in MNC, plasma and adipose tissue; subcutaneous fat mass, hepatic fat content and visceral fat mass; features of metabolic syndrome; gastric emptying, blood pressure, vascular analysis, patient reported nausea, quality of life and depression scores. Between groups comparisons will be made using students t-test or ANCOVA (adjustment will be done for baseline differences). Within group comparisons for these endpoints will be made using paired t-test or Wilcoxon's test or ANCOVA.

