17.2 If applicable, provide a power analysis.

NOTE: This may not apply to certain types of studies, including chart/records reviews, survey studies, or observational studies. This question is asked to elicit whether the investigator has an adequate sample size to achieve the study objectives and justify a conclusion.

Response: There are no prior randomized controlled trials that have examined the effect of Liraglutide on HbA1c in subjects with type 1 diabetes. In our observational study (preliminary data), we found a decrease in HbA1c of 0.35% after 6 months of liraglutide in patients with type 1 diabetes who had a mean HbA1c of $6.45\pm0.5\%$. In our proposed study, we will include patients with HbA1c up to 8.5%. Thus we expect a greater difference in HbA1c among the two groups at the end of the study. Conservatively estimating a difference in HbA1c of 0.35% between the two groups, a sample size of 32 patients per treatment group should provide 80% power to detect a significant difference ($\alpha = 0.05$), provided the standard deviation of the residuals is not greater than 0.5. Thus 64 subjects will be needed for the study. To account for a dropout rate of 30%, we will recruit 84 subjects into the study.

17.3 Describe any procedures that will be used for quality control of collected data.

Response: Three investigators and research nurse will double check the accuracy of collected data. All laboratory testing will be standardized using references and standards.

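### HbA1c change from baseline is the primary endpoint in section 2.1 but a secondary with a different test in 17.1, and baseline HbA1c is not named for the primary ANCOVA that would make the two agree

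*Combined protocol and SAP*

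**What the plan says.** - Section 2.1 gives the primary endpoint as "Change from baseline in HbA1c at 26 weeks as compared to placebo". HbA1c is not among the secondary endpoints there.
- Section 17.1 describes the primary endpoint as detecting "a difference in HbA1c after 26 weeks of treatment with Liraglutide or placebo", "using analysis of covariance (ANCOVA) and tested at the 0.05 level". It then adds: "Change in weight will be a covariate". No other covariate is named for this model. Adjustment for baseline differences appears only for the later group of non-glycemic and other secondary endpoints.
- Section 17.1 continues: "The secondary end points based on glycemic changes will include the difference from baseline in mean weekly glucose concentrations", and the same list goes on to "standard deviations of the mean weekly glucose concentrations, HbA1c, fructosamine". Between-group changes for this list are compared by Student's t-test. Within-group paired t or Wilcoxon tests are planned for the list and for the primary endpoint.
- Section 17.2 sizes the trial on a between-group difference of 0.35, with 32 per arm, 80% power, alpha 0.05 and a residual SD of at most 0.5. It does not say which model the residuals come from.
- No text ranks the HbA1c tests or controls multiplicity among them.

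**The concern.** The quantity that 2.1 calls primary is, in 17.1, a secondary endpoint with its own test. A final-value analysis and a change analysis give the same treatment estimate and p-value when both adjust for baseline HbA1c. Without that term they are different tests with different precision, and they can disagree on significance.

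Two things are at stake. The first is the protection of the single confirmatory result: someone writing the report could cite 2.1 to make the change test the headline, or 17.1 to make the week-26 ANCOVA the headline. The second is the power statement, because an SD of 0.5 means something different for a raw value, a change score and a baseline-adjusted residual.

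**Working it through.** **Inputs.** Difference 0.35, residual SD 0.5, 32 per arm and alpha 0.05 are from 17.2. The pilot HbA1c SDs of 0.5 before and 0.4 on treatment are from Table 2 in 3.1. The documents give neither the correlation r between baseline and week-26 HbA1c nor the between-patient SD in this trial's population. I assume r from 0.6 to 0.8, and SDs of 0.5 (the pilot value) and 0.8. The larger SD is considered because the pilot patients averaged 6.45%, while 6.1 admits HbA1c below 10.0% (17.2 itself speaks of up to 8.5%). Tests are taken as two-sided.

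**1. The plan's own figure.** n per arm = 2 × (1.960 + 0.842)² × 0.5² / 0.35² = 32.04. The standard error at 32 per arm is 0.5 × √(2/32) = 0.125, so 0.35/0.125 = 2.80 and power is Φ(2.80 − 1.96) = 80.0%. The exact t calculation gives 78.7%. The stated 32 and 80% reproduce, but this does not show which variable is primary.

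**2. Residual SD under each reading**, for a common SD at both time points:
- raw week-26 value: SD
- change from baseline: SD × √(2(1 − r))
- ANCOVA with baseline HbA1c: SD × √(1 − r²)

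**3. Power at 32 per arm, difference 0.35 (t-based).**

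| SD | r | Raw | Change (residual SD) | Baseline ANCOVA (residual SD) |
|---|---|---|---|---|
| 0.5 | 0.6 | 79% | 87% (0.447) | 93% (0.400) |
| 0.5 | 0.8 | 79% | 99% (0.316) | near 100% (0.300) |
| 0.8 | 0.6 | 41% | 49% (0.716) | 58% (0.640) |
| 0.8 | 0.8 | 41% | 78% (0.506) | 82% (0.480) |

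Turned round, the 0.5 ceiling in 17.2 allows these between-patient SDs:
- raw value: 0.5
- change: 0.56 to 0.79 (0.5/0.894 and 0.5/0.632)
- baseline ANCOVA: 0.63 to 0.83 (0.5/0.8 and 0.5/0.6)

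**4. Error under the null if either test could be the headline.**
- Raw value and change: the test statistics have correlation √((1 − r)/2), which is 0.447 at r = 0.6 and 0.316 at r = 0.8. The chance of at least one p below 0.05 is 9.2% and 9.5%. Simulating the week-26 ANCOVA with a weight-change covariate unrelated to HbA1c gives 8.8% at r = 0.3 and 9.5% at r = 0.9.
- Baseline-adjusted ANCOVA and t-test on change: correlation √((1 + r)/2), which is 0.894 and 0.949. The chance is 7.1% and 6.5%.
- ANCOVA on change with an unrelated weight covariate, and t-test on change: simulation gives between 5 and 6%.

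**The case against.** Section 17.1 does name one primary test. It attaches 0.05 to the ANCOVA alone and labels the t-test on change as secondary. A reader might infer two co-primary tests, each at 0.05, and therefore a trial that runs at 9% error. The documents do not say that. The 9% needs the raw-value reading of 17.1 and also the promotion of a test labelled secondary.

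Much of the text points to change. Aim 1.1 compares HbA1c before and after treatment, the paired tests need a baseline value, and the 0.35 in 17.2 comes from a within-patient fall. The 17.1 wording may simply be loose. On that reading the duplicate t-test is almost the same test as the primary, and the inflation is small. This stands as a limit on size. It does not remove the inconsistency, because HbA1c change would then be both primary by ANCOVA and secondary by t-test inside 17.1.

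Three further inferences go too far:
- **Baseline HbA1c is excluded from the model.** The text only fails to name it; "Change in weight will be a covariate" does not say it is the only covariate.
- **The 80% power is untenable for raw values.** At the only baseline SD the documents give, 0.5, raw-value power is 79%. The shortfall appears only under larger assumed SDs, where baseline adjustment does not always reach 80% either.
- **Week-12 HbA1c might enter the primary.** This would rest on "The focus of the proposed research is to evaluate the effect of liraglutide on mean HbA1c% over the period of 26 weeks of treatment", which is an introductory sentence. The endpoint statements in 2.1 and 17.1 both refer to 26 weeks.

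Under randomisation, final value and change also target the same mean treatment difference, so what is at issue is precision and the choice of test.

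**Conclusion.** The inconsistency is real and should be corrected: the primary variable in 2.1 is a secondary with another test in 17.1, and the covariate that would reconcile them is not named. If the main result could be chosen between the two tests, the error would be about 9% on the most divergent reading and about 5 to 7% if the primary is read as change or adjusted for baseline. These figures assume r from 0.6 to 0.8, two-sided tests, and a weight covariate unrelated to HbA1c where that covariate is used.

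In every row of the power table, baseline adjustment does better than the raw value or the change score. It does not by itself guarantee the stated 80%: at SD 0.8 it gives 58 to 82%. Whether 0.5 is a realistic residual SD in this population is a separate question that the documents cannot settle.

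**What to change.** 1. Use one primary definition in 2.1, 17.1 and 17.2: change from baseline in HbA1c at week 26, liraglutide versus placebo. Align the introductory sentence of 17.1 with it.
2. Analyse it by a single ANCOVA at two-sided 0.05 with baseline HbA1c as covariate. Final value and change then give the same treatment estimate and p-value.
3. Take change in weight out of the primary model. It is measured after randomisation, and section 3.1 and Hypothesis 4 expect liraglutide to alter body weight and fat, so adjusting for it can remove part of the treatment effect. Keep it as a supportive analysis only.
4. Delete HbA1c from the secondary t-test list in 17.1.
5. Label the within-group paired tests on the primary endpoint as supportive.
6. State in 17.2 that the 0.5 is the residual SD of the model in step 2.

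The cost is an amendment to the wording of these sections, with no new data, visits or patients. It should be made before any unblinded endpoint data are seen, including the half-way review of endpoint data described in 19.1 and 19.7.

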3.0 Background

3.1 Provide the scientific or scholarly background, rationale, and significance of the research based on the existing literature and how it will contribute to existing knowledge. Describe any gaps in current knowledge. Include relevant preliminary findings or prior research by the investigator.

Response: The treatment of type 1 diabetes is based on insulin replacement since the autoimmune destruction of β -cells leads to a near total loss of endogenous insulin reserve. The evolution of therapy in type 1 diabetes since the discovery of insulin in 1921 by Banting and Best has largely been based on modifications of insulin preparations or modifications of the insulin molecule (insulin analogs) to allow variable bio-availability(1, 2). Different ways of delivering insulin and monitoring glucose through subcutaneous insulin infusion pumps and continuous glucose monitoring systems have also been devised. Inspite of these advances, the control of glucose homeostasis in subjects with type 1 diabetes continues to be challenging since exogenous insulin cannot compensate totally for changing requirements and is still not precise either in terms of the dose or the bio-availability of the insulin injected (3, 4). Furthermore, in the near total absence of endogenous insulin secretion, the physiological post prandial inhibition of glucagon secretion by the α -cell is probably deficient in all type 1 diabetics, which may also contribute to the variability and unpredictability of glucose control with exogenous insulin alone(5). The concomitant use of metformin or pramlintide helps in some patients but the results are far from consistent and, therefore, these agents have not made an impact on the treatment of this condition(6). Thus, there is a need for therapies beyond insulin that can further improve glycemic control and reduce fluctuations in glucose in these subjects.

A recent trial of liraglutide, a glucagon like peptide (GLP)-1 analogue with a 24 hour duration of action, in 13 patients with type 1 diabetes led to a remarkable reduction in the excursions of blood glucose, both highs and lows, following meals and through the 24 hours within the first 2 days of treatment in all 13 subjects (7)(see preliminary data section). The mean glucose concentrations fell significantly from 136 to 111 mg/dl and the mean HbA1c fell significantly from 6.45 to 6.1% in 8 subjects who continued liraglutide for 24 weeks. The SD of glucose readings fell from 52 to 28. Remarkably, the requirement of insulin fell from 51 units to 28 units daily. The treatment also led to a reduction in appetite and to weight loss even during the short period of treatment for 9 weeks. The patients felt remarkably better and secure in terms of the 'predictability and stability' of glycemic and appetite control (7). The improvement in glycemia with the reduction in insulin requirements within days of starting treatment with liraglutide could be an evidence of insulin sensitization and /or endogenous insulinogenesis. Since C-peptide concentrations did not alter following the short term administration of liraglutide, it is likely that the suppression of glucagon may have contributed to this effect. It is also possible that the improvement in glucose homeostasis could partly have been due to a decrease in carbohydrate intake and reduced rate of gastric emptying, both of which are known actions of GLP-1 analogues (8, 9).

A recent study has shown that GLP-1 infusion suppresses basal and arginine induced glucagon secretion in subjects with type 1 diabetes(10). GLP-1 infusion also completely prevents the rise in post-prandial glucose or glucagon concentrations in these patients(11). A study by Rother et al on the effect of exenatide after a meal also showed a trend towards a reduction in the increase of glucagon after a meal for the first 45 min although there was no significant overall effect(12). In view of the 24 hour duration of action of liraglutide, it is possible that it may exert a protracted suppressive effect on glucagon and thus, decrease post prandial increases in glucagon concentrations which in turn would reduce post prandial excursions of glucose. The importance of glucagon in inducing hyperglycemia is further strengthened by the observation that glucagon receptor knockout mice do not develop diabetes inspite of complete β cell destruction by streptozotocin(13). Fasting as well as postprandial blood sugar concentrations were normal in these animals.

Our recent observations, mentioned above and described in greater detail below, could provide a potentially potent and significant advance in the treatment of type 1 diabetes if our investigations demonstrate that the use of liraglutide, a GLP-1 agonist, not only reduces glycemia but it reduces the magnitude of excursions of glucose even in stable, well controlled type 1 diabetics. This study will be the first randomized controlled prospective double blind study investigating the effect of liraglutide in such patients. If this drug is shown to be consistently effective, it will provide a major advance in the treatment of hyperglycemia and unpredictable alterations in glucose concentrations in type 1 diabetes, a disease that is newly diagnosed in 15000 children per year in the US and currently affects 3 million Americans(14).

Innovation rationale, and significance

1. This will be the first prospectively randomized controlled study to investigate the effect of liraglutide on glycemic levels and variability in overweight and obese type 1 diabetes treated with insulin alone. Liraglutide is the preferred agent for this study since its pharmacokinetics and pharmacodynamics ensure a duration of action of 24 hours. Hitherto, the treatment of type 1 diabetes is based on insulin replacement with novel analogs with appropriate pharmacodynamic profiles or with unique insulin delivery systems. The concomitant use of metformin or pramlintide helps in some patients but the benefits are far from consistent and, therefore, these agents have not made an impact on the treatment of this condition(6).
2. This will be the first study to investigate the role of glucagon and the potential basal and postprandial suppression of glucagon by liraglutide in the pathogenesis and control of glycemia in type 1 diabetics. This is particularly important since in the absence of insulin secretion from the β -cell, there is no paracrine inhibition of glucagon secretion by the α -cell. GLP-1 analogs are known to suppress glucagon(5).
3. With the use of CGM, this study will determine the rapidity of response by liraglutide, which in our preliminary study was observed within the first two days such that we advised patients to reduce their insulin doses by 25% in advance.
4. This will be the first study to attempt to reduce body weight and other features of the metabolic syndrome, while improving glycemic control with addition of a single therapeutic agent in overweight and obese patients with type 1 diabetes. This is particularly relevant since insulin induces weight gain and 40-50% of type 1 diabetics in the US have the metabolic syndrome(14). Liraglutide and the only other licensed drug in this class, exenatide, have been shown not only to reduce body weight but also

to reduce systolic blood pressure plasma triglyceride and CRP concentrations in subjects with type 2 diabetes(8; 9; 15; 16; 18).

- Finally, it will allow us to assess whether liraglutide can activate the dormant β -cells which are known to survive in type 1 diabetics for a long time (19). An analysis in a subset of the study patients with detectable C-peptide will be carried out separately. This will assess the effect of liraglutide in preserving β -cells and the effect of residual β -cell function on the action of liraglutide

Liraglutide treatment in patients with type 1 diabetes

As mentioned above, the treatment of 14 type 1 diabetes patients; age (38.5 years), duration of diabetes (20 ± 4 yrs), weight (66 ± 6 kg), HbA1c% (6.5 ± 0.5 %), C-peptide (< 0.10 nmol/l), basal insulin dose of 24 ± 6 units/day, bolus insulin dose of 22 ± 4 units/day with liraglutide in addition to insulin resulted in significant reduction in fasting and mean blood glucose concentrations, insulin doses by 45%, HbA1c levels even at 24 weeks, and a reduction in appetite and caloric intake with weight loss. In addition, there was a reduction in the excursions of blood glucose concentrations, i.e., the standard deviations of blood glucose concentrations were markedly reduced. The changes were observed within 48h and improved marginally thereafter with fine tuning of insulin doses and a further reduction in these doses. The comparison of changes observed early (1 week) vs late (9 weeks) are evident in **tables 1 and 2**. These observations are noteworthy in that they were made in patients who had been well controlled, were meticulous, even obsessive, and were on CSII and CGM. They had all tried hard to improve their diabetic control by adjusting insulin doses but had not succeeded because of the induction of hypoglycemia. To establish this fact, the patients recorded their glucose concentrations for at least two weeks during which optimal control was attempted and no significant change was observed (data not shown). While our initial plan was to assess the effect with one week treatment, 7 patients wanted to continue with Liraglutide and were able to get insurance coverage for this treatment. This study was conducted to improve glycemic control in the clinic and not as a randomized or placebo controlled trial. In view of the significant effects that were observed (**Figure 1**), we now want to conduct a prospective randomized placebo controlled trial to investigate and confirm these effects of Liraglutide in subjects with type 1 diabetes.

Table 1) Effects of Liraglutide after treatment for one week (n=14)

[figure not shown]
Table 1	Before treatment	On Liraglutide	P value
Weight(kg)	66 ± 6	65 ± 5	0.22
insulin dose (basal)	24 ± 6 U/d	16 ± 6 U/d	<0.01
insulin dose (bolus)	22 ± 4 U/d	15 ± 4 U/d	<0.01
Mean Fasting Blood Glucose (mg/dl)	129 ± 10	110 ± 8	0.02
Weekly Mean Blood Glucose (mg/dl)	141 ± 20	115 ± 12	<0.01
Time spent in hypoglycemia <70 mg/dl(% time)	2.1 ± 2	2.6 ± 2	0.08
Time spent in hypoglycemia <40 mg/dl(% time)	0.12 ± 0.2	0.16 ± 0.3	0.09
Time spent in hyperglycemia > 150 mg/dl(% time)	28 ± 6	22 ± 5	0.03
Time spent in hyperglycemia >200 mg/dl(% time)	18 ± 5	9 ± 2	<0.01
Time spent in hyperglycemia >250 mg/dl(% time)	8 ± 2	1.5 ± 1	<0.01
Mean weekly SD (mg/dl)	56 ± 10	26 ± 6	<0.01

Table 2) Effects of Liraglutide after treatment for mean duration of 24 weeks (n=8)

Table 2	Before treatment	On Liraglutide	P value
Weight (kg)	68±5	64±4	0.02
HbA1c %	6.45±0.5	6.1±0.4	0.02
insulin dose (basal)	26 ± 7 U/d	13 ± 6 U/d	<0.01
insulin dose (bolus)	25 ± 4 U/d	15 ± 4 U/d	<0.01
Mean Fasting Blood Glucose (mg/dl)	125±10	107±8	0.02
Weekly Mean Blood Glucose (mg/dl)	136±20	111±12	<0.01
Time spent in hypoglycemia <70 mg/dl (% time)	2±2	2.4±2	0.10
Time spent in hypoglycemia <40 mg/dl (% time)	0.1±0.2	0.14±0.3	0.21
Time spent in hyperglycemia > 150 mg/dl(%	27± 6	20± 5	0.01
Time spent in hyperglycemia >200 mg/dl(%	17± 5	6± 2	<0.01
Time spent in hyperglycemia >250 mg/dl(%	7.5± 2	1±1	<0.01
Mean SD weekly (mg/dl)	52±10	28±6	0.01

Figure 1: Weekly continuous glucose monitoring record of one patient prior to and following 1 week of liraglutide. Note the glycemic variability (SD) and the frequency of glucose concentrations within the target range prior to and following liraglutide

Fig 1

3.2 Include complete citations or references.

Response:

1. Bliss M: Resurrections in Toronto: the emergence of insulin. *Horm Res* 64 Suppl 2:98-102, 2005
2. Hahr AJ, Molitch ME: Optimizing insulin therapy in patients with type 1 and type 2 diabetes mellitus: optimal dosing and timing in the outpatient setting. *Am J Ther* 15:543-550, 2008
3. Pickup JC, Renard E: Long-acting insulin analogs versus insulin pump therapy for the treatment of type 1 and type 2 diabetes. *Diabetes Care* 31 Suppl 2:S140-145, 2008
5. Unger RH, Orci L: Paracrinology of islets and the paracrinopathy of diabetes. *Proc Natl Acad Sci U S A* 107:16009-16012, 2010
6. Lebovitz HE: Adjunct therapy for type 1 diabetes mellitus. *Nat Rev Endocrinol* 6:326-334, 2010
